4.5. Tertiary Endpoint Analysis

4.5.1. Tertiary Efficacy Endpoints

For continuous endpoints, either an ANCOVA model using data from EAS1 or MMRM model using data from EAS2 will be performed as described in Section 4.4.2.1.

For analysis of the binary outcomes, the details are provided in the table below:

Analysis Population	All participants in EAS1 with non-missing baseline measure
Analysis Data	All non-missing observations at baseline and at time point of interest regardless of the use of study intervention or rescue medications.
Endpoint	
 Binary outcome of HbA1c <7% or ≤6.5% at time point of interest with ‘Yes’ indicating achieving HbA1c target. The composite of 
 binary outcome of HbA1c <7% at Week 26, and, binary outcome of no nocturnal level 2 hypoglycemia during treatment phase up to Week 26. The composite of 
 binary outcome of HbA1c <7% at Week 26, and, binary outcome of no level 3 severe hypoglycemia during treatment period up to Week 26 
with “Yes” indicating achieving the target (in respective endpoints defined above).

Missing Data	
 For HbA1c, missing values at the specified timepoints will be imputed using the same method for the primary endpoint (Section 4.3.2). For hypoglycemia that are included in the composite endpoints, a participant who discontinued the treatment period before Week 26 (Visit 22) is considered as a non-responder (that is, experienced the event).
Analysis Model	
These endpoints will be analyzed using a logistic regression model including independent variables of treatment, strata (country, CGM use prior to study entry [yes/no], and carbohydrate counting for prandial insulin dosing [yes/no]), and baseline HbA1c value (and, for the composite endpoint, baseline incidence of hypoglycemia and interaction between baseline HbA1c value and baseline incidence of hypoglycemia. If the model fails to converge, the interaction term will be removed). The unconditional treatment group effect will be assessed based on a robust variance estimator for g-computation estimators (Ye et al. 2023). The estimated treatment group-specific odds ratio, p-value, and 95% CI will be used for treatment comparison. The statistical inference will be based on the multiple imputation framework by Rubin (1987).

Abbreviations: EAS1 = Efficacy Analysis Set 1; HbA1c = hemoglobin A1c.

Note: Levels of hypoglycemia events and nocturnal events are defined in Section 4.6.3.1.1.

4.5.2. Tertiary Safety Endpoints

For tertiary safety measures, the details are provided in Section 4.6 and the following subsections.

4.6. Safety Analyses

Safety measures include treatment exposure, AEs, vital signs, weight, hypoglycemia, laboratory measures, and immunogenicity. All safety analyses will be based on the Safety Analysis Set

(SS). Unless otherwise specified, the safety analysis period will include both the treatment period and follow-up period.

Percentages will be calculated using the SS as the denominator. For events that are sex-specific, the denominator and computation of the percentage will include only participants from the given sex. Unless otherwise noted, Fisher's exact test will be used for the treatment comparison and risk difference and 95% confidence intervals will be provided. Additionally, an odds ratio and 95% confidence intervals will be provided for selected tables in addition to the risk difference.

For continuous safety variables (for example, laboratory measures, vital signs, and weight), descriptive statistics for the observed and change from baseline at scheduled visits during the treatment and the follow-up period will be provided. For selected laboratory measures (that is, liver enzyme tests, lipid measures), observed values, change from baseline, and percentage change from baseline will be analyzed for the log-transformed values by the MMRM model using treatment, visit, and treatment by visit as fixed effects; baseline of the dependent variable as a covariate; and compound symmetry as the variance-covariance structure. The last postbaseline observation in the study will be analyzed by the ANCOVA model with the independent variables of treatment and baseline of the dependent variable.

The incidence and event rate of participant-reported and CGM-based hypoglycemia will be summarized by treatment and analysis period for different types of hypoglycemia. Analysis details are provided in Section 4.6.3.1.

The treatment-emergent analyses will use all data in the analysis period, including scheduled and unscheduled measurements. The safety analysis period for treatment-emergent analyses starts after the first dose and ends at the last visit in the study, including the safety follow-up period.

4.6.1. Extent of Exposure

Duration of exposure to study treatment will be summarized. No p-values will be reported in these tables as they are intended to describe the study populations, rather than test hypotheses about them. Total participant-years of exposure will be reported. The number and proportion of participants falling into the following different exposure categories will also be summarized by study treatment

- $>0, \geq 30$ days, ≥ 90 days, ≥ 180 days, and ≥ 365 days, and
- >0 and <30 days, ≥ 30 and <90 days, ≥ 90 and <180 days, ≥ 180 and <365 days, and ≥ 365 days.

Exposure on study treatment will be calculated as follows:

- LY3209590: date of the last treatment administration - date of first treatment administration + 7 days.
- Insulin degludec: date of the last treatment administration - date of first treatment administration + 1 day.

Total participant-years of exposure will be calculated by the sum of duration of exposure in days divided by 365.25. The following summary statistics will be provided: n, mean, standard deviation, median, minimum, maximum, interquartile range, and total exposure (that is, total patient-years).

All participants who complete the study treatment period are required to complete a safety follow-up period, and participants who discontinue the study treatment prematurely are encouraged to remain in the study for safety monitoring. The duration on study from the first dose of study treatment to the final study disposition date will also be summarized by treatment. A listing of exposure to study treatment will be provided.

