4.1. Overall Design

This is a Phase 3, open-label, 2-arm, parallel-design, randomized control study to investigate if LY3209590 is noninferior to insulin degludec in adult participants with T1D who are treated with basal-bolus insulin MDI therapy.

The study consists of a 1-week screening period, a 2-week lead-in period, a 52-week treatment period, and a 5-week safety follow-up period.

Visit 1: Screening

Interested participants will sign the appropriate informed consent document(s) prior to initiating any procedures.

The investigator will review medical history, symptoms, risk factors, and other inclusion and exclusion criteria prior to any diagnostic procedures. If the participant is eligible after this review, then the site will perform the diagnostic procedures to confirm eligibility.

Visit 2: Lead-In

Participants will receive their glucometer, electronic study diary, and unblinded CGM system.

Participants will receive training on

- diabetes self-monitoring and management
- unblinded CGM system
- glucometer and e-diary, and
- study requirements.

Starting with Visit 2, participants will use the study-supplied glucometer, e-diary, and unblinded CGM system for diabetes management and data collection throughout the study.

Participants will continue with their current basal-bolus insulin therapy until randomization.

Treatment period

Visit 3 (Week 0): Randomization

This is the general flow for Visit 3

- study personnel confirm enrollment criteria
- participants are randomly assigned to an intervention group (LY3209590 or insulin degludec)
- study personnel complete baseline procedures and sample collection
- study personnel will provide study insulin dosing training
 - For participants randomized to LY3209590, the first dose of LY3209590 will be administered at the site by study personnel or by the participant under observation of study personnel. Insulin dose information will be entered in the e-diary.
 - For participants randomized to insulin degludec, the first dose of degludec can be administered at the site or after the visit, depending upon the usual time of basal insulin dosing.

- study personnel complete all visit procedures.

Participants assigned to insulin degludec will be treated with daily dosing of degludec after Visit 3.

Participants will be treated with insulin lispro as prandial insulin throughout the treatment period as described in Section [6.5.3](#).

Visit 4 (Week 1)

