6.6.1. Transitioning off of Study Basal Insulin

At the last treatment visit (Visit 29 [Week 52] or ET visit), the investigator will prescribe a non-study basal insulin for use during the safety follow-up period.

The investigator, in consultation with the participant, will decide on prandial insulin therapy for use during the safety follow-up period.

Study participants treated with LY3209590

Participants will administer their last dose of LY3209590 at Week 51 of the study and can begin the transition to the non-study insulins after Visit 29 (Week 52). At Visit 29 (Week 52), the investigator will review instructions for transitioning to the non-study insulins with the participant. The non-study daily basal insulin treatment should be started slowly and under regular review of glucose profiles after discontinuation of LY3209590.

Since LY3209590 has a half-life of approximately 17 days, a slow up-titration of the non-study daily basal insulin is necessary to prevent hypoglycemia due to overlapping insulin action. Non-study basal insulin would not be required until the study participant's fasting glucose is above 100 mg/dL (5.5 mmol/L), and then daily basal insulin would be initiated and adjusted based on fasting glucose, CGM profile, and hypoglycemia evaluation. The investigator should consider titration of the non-study basal insulin to reach 50% of the required daily basal insulin dose at approximately 2 weeks and 80% of the required daily basal insulin dose at approximately 4 weeks. An unscheduled visit in addition to Visit 801 may occur during this time to facilitate the transition to non-study daily basal insulin.

Study participants treated with insulin degludec

Participants assigned to the insulin degludec treatment arm will transition to their non-study basal insulin after Visit 29 (Week 52) with dose adjustment per investigator discretion based on fasting glucose, CGM profile, and hypoglycemia evaluation and in accordance with the local product label for the basal insulin.

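### The SAP's top exposure category (≥365 days) is one day longer than the 364-day treatment period, so it splits completers by dosing-day and visit timing and can show an artificial difference between arms

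*SAP*

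**What the plan says.** SAP 4.6.1 defines exposure separately by arm: for LY3209590, "date of the last treatment administration - date of first treatment administration + 7 days", and "Insulin degludec: date of the last treatment administration - date of first treatment administration + 1 day". It then counts participants by treatment in two lists, one cumulative and one of mutually exclusive bands. Both lists end at 365 days; the exclusive list closes with "≥ 180 and <365 days, and ≥ 365 days". The table is descriptive and carries no p-values.

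The dates that feed these formulas come from the protocol:

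- **LY3209590, first dose.** Protocol 4.1: "For participants randomized to LY3209590, the first dose of LY3209590 will be administered at the site", at Visit 3 (Week 0).
- **LY3209590, last dose.** Protocol 6.6.1: "Participants will administer their last dose of LY3209590 at Week 51 of the study".
- **Degludec, first dose.** Protocol 4.1: "the first dose of degludec can be administered at the site or after the visit, depending upon the usual time of basal insulin dosing".
- **Degludec, last dose.** No day is given. Protocol 6.6.1 says only that these participants "will transition to their non-study basal insulin after Visit 29 (Week 52").

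The synopsis gives a 52-week treatment period. The Schedule of Activities allows ±3 days at Visits 4 and 29, counted from Visit 3.

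**The concern.** A reader of an exposure table in a one-year trial will usually take the top band to mean treated for the full year. Here the band starts one day after the planned treatment ends, so it cuts through the completers themselves. Whether a completer falls above or below it depends on dosing frequency, the clock time of the daily dose and the exact day of a visit.

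The two arms respond differently to the same visit timing. A late Visit 29 adds daily degludec doses and so adds exposure days. It adds none on LY3209590, whose last dose stays at Week 51. In a by-arm display, a smaller LY3209590 count at ≥365 days could be misread as earlier stopping on the new drug.

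**Working it through.** Take Visit 3 as day 0.

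**1. The plan's own length.** 52 × 7 = 364 days. For LY3209590 on schedule, the last dose is on day 51 × 7 = 357, so exposure = 357 − 0 + 7 = **364 days**. The formula reproduces the 52-week period exactly; the result is one day short of 365.

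**2. Degludec at a nominal Visit 29 (day 364).** Exposure = last − first + 1. The last-dose days, and a first dose on day 1, are assumptions, because the protocol does not fix them. A last dose on the day before Visit 29 is plausible for an evening doser, since unused drug is returned at the last treatment visit (Protocol 4.1).

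| First dose | Last dose | Exposure (days) | ≥365? |
|---|---|---|---|
| day 0 | day 364 | 365 | yes |
| day 0 | day 363 | 364 | no |
| day 1 | day 364 | 364 | no |
| day 1 | day 363 | 363 | no |

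**3. Letting visits move within ±3 days.** All seven window days are taken as equally likely, which is an assumption.

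| Case | Exposure (days) | Window days reaching 365 |
|---|---|---|
| Degludec, first dose day 0, last dose on Visit 29 day | 362 to 368 | 4/7 = 57% |
| Degludec, first dose day 0, last dose the day before | 361 to 367 | 3/7 = 43% |
| Degludec, first dose day 1, last dose the day before | 360 to 366 | 2/7 = 29% |
| LY3209590, dosing weekday kept from Visit 3 | 364 | 0 |
| LY3209590, dosing weekday follows Visit 4 | 361 to 367 | 3/7 = 43% |

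The last row arises because the second LY3209590 dose is given at Visit 4, which has its own window.

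**4. Artificial gap in the ≥365 category, degludec minus LY3209590.** With degludec first dosed on day 0, the largest gap is 57% − 0% = 57 points and the smallest is 43% − 43% = 0. If every degludec participant started on day 1 and took the last dose the day before Visit 29, while LY3209590 dosing followed Visit 4, the sign would turn: 29% − 43% = −14 points. That is an extreme combination, but it shows that the direction is not guaranteed either.

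**5. Effect on the continuous summaries.** 364/365.25 = 0.9966 years and 365/365.25 = 0.9993 years: a difference of 1 day, or 1/365 = 0.27%.

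**6. Alternative cut-points.** The lowest within-window value above is 361 days on LY3209590 and 360 on degludec. A cut at ≥360 includes every case in the step 3 table. A cut at ≥361 misses only degludec first dosed on day 1 and last dosed the day before a Visit 29 held 3 days early. An LY3209590 participant who stops one weekly dose short (on schedule, last dose at Week 50) has 50 × 7 + 7 = 357 days and stays below either cut.

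**The case against.** The strongest reply is that nothing here is miscalculated. The LY3209590 formula returns 364 days for a 364-day period, placing 364 in the band below 365 is correct, and the SAP never labels ≥365 days as completion. All of that stands: the point concerns where the cut-point sits, not an error in the exposure formula.

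Several stronger readings are tempting, and the documents do not support them.

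- **No LY3209590 completer can reach 365 days.** This is true only if the dosing weekday stays fixed to Visit 3. Visit 4 may be up to 3 days late, and Protocol 6.1 lets the dosing day change if the previous dose was at least 3 days earlier. Exposure of 365 to 367 days is possible within the protocol.
- **The table will show 57% or 43% on degludec against 0% on LY3209590.** That contrast moves Visit 29 for one arm and holds the other arm rigid. It also relies on a last degludec day that the protocol does not state.
- **The table would suggest shorter follow-up.** Exposure is not follow-up. SAP 4.6.1 separately summarizes time from first dose to final study disposition, along with the mean, median, range, interquartile range and participant-years. SAP 4.2 reports completion and discontinuation of treatment and study by arm, with reasons.
- **The table is the plan's evidence of full-length treatment.** The SAP describes it as a description of the study populations and gives it no such role.

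These limits reduce the consequence. They do not remove the mismatch: an LY3209590 participant who does exactly what the protocol asks is left out of the top category, while a degludec participant who does the same may or may not be.

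**Conclusion.** The point holds as a minor one. A 365-day cut in a 364-day treatment period separates completers from one another, and it can do so unevenly by arm. The firm result is 364 days for an on-schedule LY3209590 completer, against 364 or 365 for a degludec completer first dosed on day 0 with a nominal Visit 29, and up to 368 with a late one.

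The between-arm gap in the category is possible but not established. It is about 0 to 57 percentage points under equally likely window days and a first degludec dose on day 0, and it depends on how the Visit 4 and Visit 29 windows are used and on the unstated first and last degludec days. A reader might infer that a difference favouring degludec is certain; the documents do not show that.

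The effect is confined to one category of a descriptive table. No estimand, hypothesis test or participant-year total uses it.

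**What to change.** In both lists of SAP 4.6.1, replace the 365-day cut-point with one at or just below the lower edge of the Week 52 visit window, and change the upper bound of the band beneath it to match. A cut at ≥360 days covers all the within-window cases worked through above in both arms; ≥361 is nearly as good.

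If ≥365 days is needed for other reporting, keep it, add the new category beside it, and footnote that an LY3209590 completer exactly on schedule has 364 days by the SAP formula.

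The cost is three small edits (≥365 twice, <365 once) and a cut-point that is no longer a calendar year. A degludec participant who stops a few days before Visit 29 could also be counted in the top category. Data collection, endpoints and alpha are untouched.

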4.6.2. Adverse Events

Events that are newly reported after the first dose of investigational product (IP) or are reported to worsen in severity from baseline will be considered treatment-emergent AEs (TEAEs). The Medical Dictionary for Regulatory Activities (MedDRA) Lowest Level Term (LLT) will be used in the treatment-emergent assessment. The maximum severity for each LLT during the baseline period (see the table in Section 4.1) will be used as baseline severity.

The table below describes the analyses related to AEs.

Analysis	Details
Overview of AEs	
 number and percentage of participants who experienced SAEs deaths discontinuation from the study treatment due to an AE discontinuation from the study due to an AE TEAEs, and TEAEs related to study treatment.
Summary by PT within SOC	
 TEAEs Maximum Severity TEAEs SAEs, and AE leading to permanent discontinuation of study treatment. 
Events will be ordered by decreasing risk difference within SOC. SOCs will be listed by decreasing risk difference.
 
For each participant and TEAE, the maximum severity for the MedDRA PT is the maximum postbaseline severity observed from all associated LLTs mapping to the MedDRA PT. The maximum severity will be determined based on the non-missing severities.

Summary by PT (within SMQ when applicable)	Number and percentage of participants with TEAEs using MedDRA PT (irrespective of SOC) 
 TEAEs occurring in $\geq 1\%$ before rounding in LY3209590 group. Events will be ordered by decreasing risk difference and by decreasing frequency in LY3209590 group, respectively. TEAE of safety topic of interest by PT (within SMQ when applicable). Events will be ordered by decreasing risk difference.
Listing	Separate listings for the following events will be provided: 
 SAEs including death. AEs leading to study treatment discontinuation severe hypoglycemia events sent to the external adjudicator for MACE adjudication participants who receive rescue therapy due to severe/persistent hyperglycemia persistent-recurrent hypoglycemia reported by investigators persistent-recurrent hypoglycemia identified by programming, and medication errors of interest.

Abbreviations: AE = adverse event; LLT = lowest level term; MACE = major adverse cardiovascular event; MedDRA = Medical Dictionary for Regulatory Activities; PT = Preferred Term; SAE = serious adverse event; SMQ = Standardised MedDRA query; SOC = System Organ Class; TEAE = treatment-emergent adverse event.

4.6.2.1. Safety Topics of Special Interest

4.6.2.1.1. Severe Hypoglycemia

Severe hypoglycemia is a severe event characterized by altered mental and/or physical status requiring assistance for treatment of hypoglycemia. The determination of a hypoglycemic event as an episode of severe hypoglycemia is made by the investigator based on the medical need of the participant to have required assistance and is not predicated on the report of a participant simply having received assistance. If a hypoglycemic event meets the criteria of severe hypoglycemia, the investigator must record the event as serious on the AE case report form (CRF).

A summary of severe hypoglycemia by Preferred Term (PT) will be provided. The incidence and event rate during the treatment period will be analyzed using the method described in Section 4.6.3.1.1. A listing of severe hypoglycemia events will also be provided.

4.6.2.1.2. Persistent-Recurrent Hypoglycemia

The potential risk of persistent-recurrent hypoglycemia (P-R hypoglycemia) will be assessed from the first dose date up to the end of the study. P-R hypoglycemia events will be identified using:

- a prespecified criteria to derive events from the e-diary database (see definition in Appendix 10 [Section 6.10]), and
- investigator assessment and clinical judgment to determine if the participant experienced repeated hypoglycemia.

Identification of P-R hypoglycemia based on investigator reporting is precipitated by a hypoglycemic event a participant reported having a potential clinical treatment or outcome. This information will trigger an e-mail alert notifying the investigator to evaluate the event. Hypoglycemic events that trigger alerts to investigators are those in which participants report in the e-diary having required treatment with glucagon or intravenous glucose, resulted in coma, motor vehicle accident or other trauma, hospitalization, or emergency medical care.

Upon receiving the e-mail notification, the investigator will access the e-diary database and answer the following question: *"In your clinical judgement, is this hypoglycemia event associated with repeated hypoglycemia events?"* The investigator should select "Yes" or "No" as an answer.

P-R hypoglycemia events and participants who experience P-R hypoglycemia will be identified by one or both of the approaches explained above. Summary statistics and a listing of the events identified by both methods will be provided.

4.6.2.1.3. Systemic Hypersensitivity Reactions

Hypersensitivity reactions are exaggerated or inappropriate immunologic responses occurring in response to an antigen or allergen. These can be systemic or localized. At all visits, participants

will be evaluated by the investigator for signs and symptoms suggestive of hypersensitivity. Investigators will complete a CRF designed to record additional information about AEs suggestive of a hypersensitivity reaction. The TEAEs of hypersensitivity reactions were identified using:

- *Anaphylactic reaction* SMQ (20000021; narrow terms)
- *Hypersensitivity* SMQ (20000214; narrow terms), and
- *Angioedema* SMQ (20000024; narrow terms).

The number and percentage of participants reported with a TEAE for the following will be analyzed:

- any narrow term from any 1 of the 3 SMQs indicated above (that is, combined search across narrow portions of all 3 SMQs), and
- any narrow term within each SMQ, separately (that is, narrow SMQ search).

Individual PTs that satisfied the query will appear in the summary nested within each SMQ in decreasing order of risk difference.

The analyses above are the starting point for medical interpretation of any apparent differences between treatment groups. For notable events, case review will be applied to make the final determination of whether an event is most accurately described as a potential hypersensitivity reaction to study treatment or another event that is not clearly associated with study treatment administration. This judgment will be on the basis of totality of information available, including the content of a follow-up CRF collected for potential hypersensitivity events.

4.6.2.1.4. *Injection Site Reactions*

Injection site reactions (ISRs) are AEs localized to the immediate site of the administration of a medication. The evaluation of ISRs will be through the unsolicited reporting of ISR TEAEs and through the use of an ISR follow-up form completed by the investigator for each incidence of an ISR considered by the investigator to be related to study basal insulin. A summary of the number of participants with reported events meeting any of the following categories will be provided:

- MedDRA High Level Term (HLT) of Injection site reactions
- MedDRA HLT of Administration site reactions NEC, and
- lipodystrophies and localized amyloidosis, as represented by PTs of
 - *Lipoatrophy*
 - *Lipodystrophy acquired*
 - *Partial lipodystrophy*
 - *Lipohypertrophy*
 - *Sclerema*, and
 - *Cutaneous amyloidosis*.

The summary will present

- the number of participants reporting at least 1 AE meeting any of the above categories
- the number of participants reporting any AE in each category, and
- the number of participants reporting any AE for each PT within a specific category.

The PTs will be listed for summary within each category in decreasing order of risk difference.

The additional data collected on the ISR follow-up forms will be summarized in 2 distinct ways:

1. at the participant-level (each participant contributes to totals at most once, regardless of the number of ISR events the participant experienced), and
2. at the event level (each separate event contributes to totals, regardless of whether the participant experienced multiple ISR events).

4.6.2.1.5. *Neoplasms*

The TEAEs of neoplasms will be identified by narrow search for the following SMQs:

- *Malignant tumours* SMQ (20000194, narrow terms), and
- *Tumours of unspecified malignancy* SMQ (20000195, narrow terms).

A summary will present

- any narrow term from any 1 of the 2 SMQs indicated above (that is, combined search across narrow portions of both SMQs), and
- any narrow term within each SMQ, separately (that is, narrow SMQ search).

4.6.2.1.6. *Diabetic Ketoacidosis*

Diabetic ketoacidosis (DKA) will be searched by MedDRA PTs from all TEAEs. The number and percentage of participants experiencing treatment-emergent DKA will be summarized by PT and treatment. The following PTs will be used in search of DKA:

- *Diabetic ketoacidosis*
- *Ketoacidosis*
- *Euglycaemic diabetic ketoacidosis*
- *Ketonuria*
- *Diabetic ketosis*
- *Diabetic ketoacidotic hyperglycaemic coma*
- *Ketosis*
- *Urine ketone body present*
- *Blood ketone body*
- *Blood ketone body increased*
- *Urine ketone body*
- *Blood ketone body present, and*
- *Lactic acidosis.*

4.6.2.1.7. *Diabetic Retinopathy or Maculopathy*

Diabetic retinopathy or Maculopathy will be searched by MedDRA PTs from all TEAEs. The list of PTs for the search is provided in Appendix 7 (Section 6.7). A summary of treatment-emergent retinopathy or maculopathy by PT will be provided.

